## Appendix B: New York Heart Association (NYHA) Classification of Cardiac Disease

The following table presents the NYHA classification of cardiac disease.

| Class | Functional Capacity  | Objective Assessment  |
|-------|--|---|
| I     | Patients with cardiac disease but without resulting limitations of physical activity. Ordinary physical activity does not cause undue fatigue, palpitation, dyspnea, or anginal pain.  | No objective evidence of cardiovascular disease.                |
| II    | Patients with cardiac disease resulting in slight limitation of physical activity. They are comfortable at rest. Ordinary physical activity results in fatigue, palpitation, dyspnea, or anginal pain.   | Objective evidence of minimal cardiovascular disease.           |
| III   | Patients with cardiac disease resulting in marked limitation of physical activity. They are comfortable at rest. Less than ordinary activity causes fatigue, palpitation, dyspnea, or anginal pain.  | Objective evidence of moderately severe cardiovascular disease. |
| IV    | Patients with cardiac disease resulting in inability to carry on any physical activity without discomfort. Symptoms of heart failure or the anginal syndrome may be present even at rest. If any physical activity is undertaken, discomfort is increased. | Objective evidence of severe cardiovascular disease.            |

Source: The Criteria Committee of New York Heart Association. Nomenclature and Criteria for Diagnosis of Diseases of the Heart and Great Vessels. 9th Ed. Boston, MA: Little, Brown & Co; 1994:253-256.

## Appendix C: Guidelines for Female Patients of Childbearing Potential and Fertile Male Patients

### **Acceptable Contraception Methods:**

Women of childbearing potential (WoCBP), defined as all women physiologically capable of becoming pregnant, must use highly-effective contraception during the study and until 2 days following the last dose of acalabrutinib. For male subjects with a pregnant or non-pregnant WoCBP partner, no contraception measures are required.

Highly effective contraception is defined as either:

|                                   |   |
|-----------------------------------|---|
| True Abstinence            | When this is in line with the preferred and usual lifestyle of the patient during the entire period of risk associated with the study drug. Periodic abstinence (e.g., calendar, ovulation, symptothermal, post-ovulation methods) and withdrawal are not acceptable methods of contraception.  |
| Sterilization              | When a WoCBP has had surgical bilateral oophorectomy (with or without hysterectomy) or tubal ligation at least six weeks prior to study entry. In case of oophorectomy alone, only when the reproductive status of the woman has been confirmed by follow-up hormone level assessment.          |
| Female condom              | Barrier methods of contraception: condom or an occlusive cap (diaphragm or cervical/vault caps) with spermicidal foam/gel/film/cream/vaginal suppository.   |
| Male Partner Sterilization | With the appropriate post-vasectomy documentation of the absence of sperm in the ejaculate.   |
| Intrauterine device        | Placement of an intrauterine device (IUD) or intrauterine system (IUS)  |
| Hormonal contraception     | Combined (estrogen and progestogen containing) hormonal contraception associated with inhibition of ovulation, which may be oral, intravaginal, or transdermal. Progestogen-only hormonal contraception associated with inhibition of ovulation, which may be oral, injectable, or implantable. |

Hormonal contraception may be susceptible to interaction with the study drug or other drugs, which may reduce the efficacy of the contraception method.

If a contraceptive method is restricted by local regulations/guidelines, then it does not qualify as an acceptable highly effective method of contraception for subjects participating at sites in the relevant country/region.

Subjects should promptly notify the Investigator if they, or for male subjects their partner, become pregnant during this study, or within 2 days after the last dose of acalabrutinib. If a female subject becomes pregnant during the treatment period, she must discontinue acalabrutinib immediately. Pregnancy in a female subject or a male subject's partner must be reported as outlined in Section 11.3.8.

**Acceptable forms of barrier contraception include:**

- Latex condom, diaphragm or cervical/vault cap when used with spermicidal foam/gel/film/cream/suppository

**Unacceptable methods of contraception include:**

- Periodic abstinence
- Natural family planning (rhythm method) or breastfeeding
- Fertility awareness
- Withdrawal
- Triphasic combined oral contraceptives
- All progesterone only pills, except Cerazette™
- All barrier methods, if intended to be used alone
- Non-copper containing intrauterine devices

**Pregnancies**

To ensure patient safety, each pregnancy in a patient on the study drug must be reported to the Innovations Safety Department within 24 hours of learning of its occurrence. The pregnancy should be followed up for 3 months after the termination of the pregnancy to determine outcome, including spontaneous or voluntary termination, details of the birth, and the presence or absence of any birth defects, congenital abnormalities, or maternal and/or newborn complications.

Pregnancy should be recorded on a Clinical Study Pregnancy Form and reported by the Investigator to the Innovations Safety Department. Pregnancy follow-up should be recorded on the same form and should include an assessment of the possible relationship to the study drug of any pregnancy outcome. Any SAE experienced during pregnancy must be reported on the SAE Report Form.

Pregnancy outcomes must be collected for the female partners of any males who took the study drug in this study. Consent to report information regarding these pregnancy outcomes should be obtained from the mother.

**Women Not of Childbearing Potential are Defined as Follows:**

- Women are considered post-menopausal and not of childbearing potential if they have had 12 months of natural (spontaneous) amenorrhea with an appropriate clinical profile (i.e., age appropriate, history of vasomotor symptoms).
- Women <45 years of age a high follicle-stimulating hormone (FSH) level in the postmenopausal range may be used to confirm a post-menopausal state in women not using hormonal contraception or hormonal replacement therapy. In the absence of 12 months of amenorrhea, a single FSH measurement is insufficient.

- Women who are permanently sterilized at least 6 weeks before screening (e.g., bilateral tubal ligation/occlusion, hysterectomy, bilateral salpingectomy, bilateral oophorectomy).
- Women who are >45 years-of-age, not using hormone-replacement therapy and who have experienced total cessation of menses for at least 1 year OR who have a FSH value >40 mIU/mL and an estradiol value <40 pg/mL (140 pmol/L).
- Women who are >45 years-of-age, using hormone-replacement therapy and who have experienced total cessation of menses for at least 1 year OR who have had documented evidence of menopause based on FSH >40 mIU/mL and estradiol <40 pg/mL prior to initiation of hormone-replacement therapy.
- Women who had have a congenital or acquired condition that prevents childbearing.

## Appendix D: Schedule of Assessments

| ASSESSMENTS                                       | Screening |                       | Acalabrutinib Maintenance post-BMT a                   |              |  |   |   | End of treatment visit g | Follow-Up h |
|---|-----------|-----------------------|---|--------------|--|---|---|-------------------------------------|------------------------|
|   | Pre-BMT   | Post-BMT b | Cycle1 c
~4 mos.
Post-BMT                        |              | Cycles 2-6 d
~5-9 mos.
post-BMT | Cycles 7-12 e
~10-15 mos.
post-BMT | Cycles 13 & beyond f
≥16 mos.
post-BMT |                                     |                        |
|   |           | D1                    | D15   | D1 (±7 days) |  | D1 (±7 days)  | D1  |                                     |                        |
| Medical history & demographics         | X         |                       |   |              |  |   |   |                                     |                        |
| Physical examination & weight          | X         | X                     | X   | X            | X  | X   | X   |                                     |                        |
| ECOG PS                                    |           | X                     | X   |              | X  | X   | X   |                                     |                        |
| Vital signsi                    |           | X                     | X   |              | X  | X   | X   |                                     |                        |
| ECGj                            |           | X                     |   |              |  |   |   |                                     |                        |
| CBC & CMP                              |           | X                     | X   | X            | X  | X   | X   |                                     |                        |
| Coagulation testingu            |           | X                     |   |              |  |   |   |                                     |                        |
| Urinalysis                                 |           | X                     |   |              |  |   |   |                                     |                        |
| Pregnancy testk                 | X         | X                     |   |              |  |   |   |                                     |                        |
| HIV testl                       |           | X                     |   |              |  |   |   |                                     |                        |
| Hepatitis B virus PCRm          |           | X                     |   |              | X m                                   | X m                                      | X m  | X m                      |                        |
| Hepatitis C virus PCRn          |           | X n        |   |              |  |   |   |                                     |                        |
| Archival tumor sampleo          | X         | X o        |   |              |  |   |   |                                     |                        |
| Fresh tumor biopsiesp           |           |                       |   |              |  |   |   | X p                      | X p         |
| MRD analysis (blood)q           |           | X q        |   |              | X q                                   | X q                                      | X q  |                                     |                        |
| MRD analysis (BM aspirate)r     |           | X r        |   |              |  | X r                                      |   |                                     |                        |
| CT/MRI/PETs                     |           | X                     |   |              | X s                                   | X s                                      | X s  |                                     |                        |
| Acalabrutinib (oral) & drug compliance |           |                       | 129 mg twice daily continuously for 2 years post-BMT (~22 cycles) |              |  |   |   |                                     |                        |
| Concomitant medications                    | X         | X                     | X   | X            | X  | X   | X   | X                                   |                        |
| AE evaluationst                 |           |                       | X   | X            | X  | X   | X   | X                                   |                        |
| PFS follow-up                              |           |                       |   |              |  |   |   |                                     | X                      |

- a. Acalabrutinib maintenance therapy begins on Day 100 post-BMT
- b. Post-BMT screening should occur between Day +80 and Day +100
- c. Begin between Day +100 and Day +120
- d. Clinic visits will be monthly on Day 1 for Cycles 2-6 only (See Planned Clinic Visits table below)
- e. Cycles 7-12 only: clinic visits will **occur every 2 months for 6 months** (See Planned Clinic Visits table below)
- f. Cycle 13 and beyond until 5 years post-BMT: **clinic visits will occur every 3 months** (See Planned Clinic Visits table below)
- g. Within 30 days of last dose of acalabrutinib
- h. A telephone call to assess PFS every 3 months can be made in lieu of an office visit
- i. Blood pressure, pulse, oxygen saturation, and temperature
- j. Subjects should be in supine position and resting for at least 10 minutes before any study-related ECGs are taken.
- k. For women of childbearing potential only at the time of screening (post- and prior to BMT) and 72 hours before the start of treatment. Urine or serum pregnancy tests are acceptable.
- l. Patients with a known history of human immunodeficiency virus (HIV) or who are HIV antibody positive should be tested for HIV RNA during screening. No further testing beyond screening is necessary if PCR results are negative, except if clinically indicated (see Section 6.5.6).
- m. Only patients who are anti-HBc positive, or have a known history of HBV, should have quantitative PCR testing for HBV DNA performed during screening and every 3 months thereafter. Monitoring (every 3 months) should continue until 12 months after last dose of acalabrutinib. As IVIG may cause false positive hepatitis serology, monthly PCR testing is not required in patients who are currently receiving or received prophylactic IVIG within 3 months before study enrollment and have a documented negative anti-HBc test before the initiation of IVIG therapy (see Section 6.5.6).
- n. Patients with a known history of hepatitis C virus (HCV) or who are hepatitis C antibody positive should be tested for HCV RNA during screening. No further testing beyond screening is necessary if PCR results are negative, except if clinically indicated (see Section 6.5.6).
- o. If not obtained during Screening #1 (prior to BMT)
- p. Collect a fresh lymphoma biopsy at disease progression
- q. **MRD analysis with blood sample:** Collect a blood sample prior to beginning maintenance on Day +100 (Screening #2), 6 months (~Cycle 4 Day 1), 1 year (~Cycle 10 Day 1) and 2 years post-BMT (~Cycle 22 Day 1).
- r. **MRD analysis with bone marrow biopsy and aspirate:** Collect a bone marrow biopsy and aspirate prior to beginning maintenance on Day +100 (Screening #2) and at 1 year post-BMT (~Cycle 10 Day 1).
- s. CT/MRI/FDG-PET scans will be done post-BMT (Day 80-100), at 6 months, 12 months, 18 months and 24 months. Thereafter, scans will be done per institutional standard operating procedures.
- t. Record all AEs regardless of seriousness or relationship spanning from the first dose of acalabrutinib until 30 calendar days after discontinuation or completion of study drug.
- u. Coagulation testing will include PT/INR or aPTT.

## Planned Clinic Visits

| Cycle 1  |           | d. Cycles 2-6 only:
clinic visits will occur every month |          |                                    |          |          |             | e. Cycles 7-12 only:
clinic visits will occur every 2 months |             |                                     |             |           |                                  | f. Cycle 13 and beyond until 5 years post-BMT:
clinic visits will occur every 3 months |             |                                     |             |             |           |             |             |                                     |  |
|----------|-----------|---|----------|------------------------------------|----------|----------|-------------|---|-------------|-------------------------------------|-------------|-----------|----------------------------------|---|-------------|-------------------------------------|-------------|-------------|-----------|-------------|-------------|-------------------------------------|--|
| C1
D1 | C1
D15 | C2
D1  | C3
D1 | C4
D1                           | C5
D1 | C6
D1 | C7
D1    | C8
D1  | C9
D1    | C10
D1                           | C11
D1   | C12
D1 | C13
D1                        | C14
D1   | C15
D1   | C16
D1                           | C17
D1   | C18
D1   | C19
D1 | C20
D1   | C21
D1   | C22
D1                           |  |
| Visit    | Visit     | Visit   | Visit    | Required
for
6 mo
imaging | Visit    | Visit    | No
Visit | Begin
every
2 mo
visits                                | No
Visit | Required
for
12 mo
imaging | No
Visit | Visit     | Begin
every
3 mo
visits | No
Visit   | No
Visit | Required
for
18 mo
imaging | No
Visit | No
Visit | Visit     | No
Visit | No
Visit | Required
For
24 mo
imaging |  |

## Appendix E RECIL 2017: Response Categories Based on Assessment of Target Lesions

| % Change in sum of diameters of target lesions from nadir |  |  |   |   |   |
|---|--|--|---|---|---|
|   | CR  | PR  | MRa   | SD   | PD   |
| % change from baseline                                    | Complete disappearance of all target lesions and all nodes with long axis <10mm.
≥30% decrease in the sum of longest diameters of target lesions (PR) with normalization of FDG-PET | ≥30% decrease in the sum of longest diameters of target lesions but not a CR | ≥10% decrease in the sum of longest diameters of target lesions but not a PR (<30%) | <10% decrease or ≤ 20% increase in the sum of longest diameters of target lesions | >20% increase in the sum of longest diameters of target lesions
For small lymph nodes measuring <15 mm post therapy, a minimum absolute increase of 5 mm and the long diameter should exceed 15 mm
Appearance of a new lesion |
| FDG-PET   | Normalization of FDG-PET (Deauville score 1-3)   | Positive (Deauville score 4-5)   | Any   | Any   | Any   |
| Bone marrow involvement                                   | Not involved   | Any  | Any   | Any   | Any   |
| New lesions   | No   | No   | No  | No  | Yes or No   |

a A provisional category

Abbreviations: CR, complete response; CT, compute tomography; FDG-PET, [18F]2-fluoro-2-deoxy-D-glucose; MR, minor response; PD, disease progression; PR, partial response; SD, stable disease.

Source: Younes et al 2017

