### **6.5.14 Radiologic Assessments**

Response assessments will be evaluated based on recent International Working Group consensus criteria Response Evaluation Criteria in Lymphoma (RECIL 2017) (Younes et al 2017), outlined in Appendix E and Appendix F.

Tumor assessments will be performed using radiologic imaging by CT scan with contrast covering neck, chest, abdomen, and pelvis and [F]2-fluoro-2-deoxy-D-glucose-positron emission tomography (FDG-PET) scan covering from base of skull to mid-thigh within 28 days before the first dose of study drug and as outlined in Appendix D. In certain cases, measurements may be performed on the CT component of a combined PET-CT image, provided that is of adequate resolution. In the latter instance, approval by the sponsor is required.

Magnetic resonance imaging (MRI) may be used for imaging assessments if a contrast CT scan is contraindicated or undesirable. In cases where MRI is desirable, the MRI must be obtained at baseline and at all subsequent response evaluations.

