## **9. RESPONSE EVALUATIONS AND MEASUREMENTS**

### **9.1 Progression-free Survival**

Progression-free survival is defined as the time from Day 0 of BMT until the date of objective radiological PD according to RECIL or death (by any cause in the absence of PD). Patients who are alive and free from PD will be censored at the date of last tumor assessment. Patients who begin subsequent therapy prior to PD or death will be censored at the date of last tumor assessment prior to the start of subsequent therapy.

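### Appendix E gives two reference points, nadir and baseline, for the 20% size increase that defines progression, a component of the primary PFS event

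*Combined protocol and SAP*

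**What the plan says.** - Section 9.1 runs PFS from Day 0 of BMT "until the date of objective radiological PD according to RECIL", or death. Section 10.4.2 also defers to RECIL. Section 10.2 makes the primary endpoint the percentage alive and free of progression or relapse at 2 years post-BMT.
- Section 6.5.14 adopts RECIL 2017 as "outlined in Appendix E and Appendix F", so those tables are what sites will use.
- Appendix E is headed "Change in sum of diameters of target lesions from nadir". The row that contains the CR, PR, MR, SD and PD size criteria is labelled "change from baseline".
- In that row the PD cell reads ">20% increase in the sum of longest diameters of target lesions" and the SD cell reads "<10% decrease or ≤ 20% increase in the sum of longest diameters of target lesions". Neither names its reference. The PD cell adds a condition for nodes under 15 mm after therapy (growth of at least 5 mm, and a long diameter above 15 mm). It also counts "Appearance of a new lesion" as PD.
- Appendix F takes the target-lesion category as an input. A new lesion or nontarget progression is PD whatever the target lesions show.
- Appendix D, footnote s, schedules scans at Day 80-100 and at 6, 12, 18 and 24 months, then by institutional practice.

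The word nadir occurs only in the Appendix E header. The lesion-selection text in Section 6.5.14 defines the sum of longest diameters but gives no reference for change.

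**The concern.** One row of thresholds cannot sensibly have both references. PR and MR are decreases and have meaning only against baseline; a fall measured from the smallest sum so far does not describe a response. For an increase, the two references agree only while the sum has never fallen below baseline. After any shrinkage they give different thresholds.

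The protocol allows for such patients. Sections 3.1 to 3.3 exclude progression but do not require CR, so patients may enter with measurable lesions. Section 6.5.9 foresees patients who respond on the drug and relapse later. About 10 sites will make the calls, and the documents describe no central imaging review. A site that follows the row label as printed would leave a regrowing patient in MR or SD. The event would be dated at a later scan or missed, and an error in that direction favours the drug in a trial with no comparator.

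**Working it through.** **Planned precision, for scale.** Section 10.2 gives 65%-90% for an observed 80% of 45. The exact (Clopper-Pearson) interval for 36/45 is 65.4%-90.4%, so that figure reproduces. Inflating 45 for 10% non-evaluable gives 45/0.9 = 50. Neither figure is in dispute here.

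**Growth needed before PD.** Let *s* be the fraction by which the sum has shrunk from baseline at its smallest.

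- Header reading (nadir): PD above 1.2 × (1 − *s*) of the baseline sum.
- Row reading (baseline): PD above 1.2 of the baseline sum.
- Growth from nadir needed under the row reading: 1.2/(1 − *s*) − 1.

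| Shrinkage *s* | PD threshold, nadir (% of baseline sum) | PD threshold, baseline | Growth from nadir needed, nadir reading | Growth from nadir needed, baseline reading |
|---|---|---|---|---|
| 0% | 120 | 120 | 20% | 20% |
| 20% | 96 | 120 | 20% | 50% |
| 30% | 84 | 120 | 20% | 71% |
| 40% | 72 | 120 | 20% | 100% |
| 50% | 60 | 120 | 20% | 140% |

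**Example (assumed sizes, one lesion).** Baseline 40 mm, nadir 24 mm, next scan 32 mm.

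- From nadir: (32 − 24)/24 = +33%, which is PD.
- From baseline: (32 − 40)/40 = −20%, which falls in the MR range.

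**Small nodes.** The gap is narrower where the small-node condition applies. A single 15 mm node that shrinks to 10 mm must exceed 15 mm under the nadir reading, which is +50% from nadir. Under the baseline reading it must exceed 1.2 × 15 = 18 mm, which is +80%. The 40/24/32 mm sums also give a different answer if they come from two nodes of 20, 12 and 16 mm each. Each node then grows by 4 mm, short of the 5 mm minimum, so the patient would not be PD even from nadir.

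**Effect on the 2-year rate.** With follow-up complete to 2 years, a call made late but still inside 2 years (for example at 18 instead of 12 months) moves the PFS date but not the 2-year rate. The rate moves only if the patient stays at or below 120% of the baseline sum through the 24-month scan, with no new lesion, nontarget progression or death. Each such patient adds 1/45 = 2.2 points. As an illustration from a true 36/45:

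| Missed events | Rate | Exact 95% CI |
|---|---|---|
| 0 | 80.0% | 65.4-90.4 |
| 1 | 82.2% | 67.9-92.0 |
| 2 | 84.4% | 70.5-93.5 |
| 3 | 86.7% | 73.2-94.9 |

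The counts of 1 to 3 are assumptions. The standard error at 80% is √(0.8 × 0.2/45) = 6.0 points.

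**The case against.** Four objections deserve an answer.

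1. **Layout.** The header may have spanned only some columns before the PDF was read. That cannot be excluded. But both labels are current text in one table, the PD threshold sits in the row labelled from baseline, and no other section decides between them.
2. **RECIL itself governs.** Sections 9.1 and 10.4.2 define progression by RECIL, and a reader who knows the source may supply the reference. The publication is not part of the documents, and Section 6.5.14 directs sites to the appendices, so the table should be right as printed.
3. **Only one reading is coherent.** Decreases from baseline and increases from nadir would use both labels, and the small-node clause, with its post-therapy size, hints at nadir for PD. This makes the intended meaning likely. It does not state it, and the harmful reading is simply the row label taken literally.
4. **Few patients.** To affect the primary rate a patient must have a target lesion of at least 15 mm at Day 80-100, shrink, regrow in the same lesions only, and stay within the baseline limit to 24 months. Section 1.1 describes the disease as aggressive in most patients, so this path may be narrow. This objection stands and limits the size of the point.

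**Conclusion.** The contradiction is real and concerns a component of the primary event. After 20% to 50% shrinkage, the row label requires 50% to 140% regrowth from nadir against 20% under the header, with a smaller gap for small nodes. Each patient carried past the 24-month scan adds 2.2 points at 45 patients. Upward bias arises only where the baseline label is applied to PD. Patients with no target lesions are unaffected.

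A reader might infer that the primary rate is inflated by several points. Assuming, say, that 5 to 14 of 45 patients have residual target lesions and that 10% to 30% of those cross the 2-year mark gives 0.5/45 to 4.2/45, about 1 to 9 points. Neither input is in the documents, so this is not an estimate of bias. Nor do the documents support the inference that every late call raises the 2-year rate, or that sites will in fact use the baseline label. The supported conclusion is an event rule open to two readings, with an effect of unknown and possibly small size. It should be corrected before analysis.

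**What to change.** For endpoint derivation, reconcile the two labels in Appendix E:

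- Decrease thresholds (PR, MR and the decrease bound of SD): percentage change from baseline, meaning the Day 80-100 scan.
- Increase thresholds (SD's upper bound of 20% and PD's more than 20%): percentage change from nadir, defined as the smallest sum on study including baseline.
- Keep the small-node condition as it is.

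Both increase bounds need the same reference; otherwise SD and PD would no longer meet at 20%. If target-lesion sums are recorded in the eCRF, which the documents do not say, check the sites' PD calls against them.

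Progression is also a reason to stop study drug in Section 3.4. This proposal covers only how the endpoint is derived and does not address treatment decisions.

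The cost is the wording of one table and, where the data exist, a derivation check. The 45 evaluable, the total of 50 and the planned interval are unchanged. The 2-year rate may come out slightly less favourable.
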